95 intake. Furthermore, it is unknown how long any effect of increased EE due to cold exposure on
96 energy intake would persist. For example, the energy deficit created by the cold-induced
97 thermogenesis may lead to a hunger signal that persists even with a return to thermoneutral
98 temperatures. Alternatively, the increase in EE from the cold-induced thermogenesis may directly
99 stimulate food-seeking behavior. If there is a direct effect of an EE increase, it is unclear if it would
100 exist only during cold exposure or if it would persist even after a return to more comfortable
101 temperatures.

102 **Possible Mediators of the Energy Expenditure to Energy Intake Link**

103 The signals from lean tissue that might indicate energy needs to the orexigenic centers of the
104 brain are largely unknown. One possibility is hormonal signals. Hormones that may be potential
105 transmitters of energy needs include myokines released from skeletal muscle or other factors
106 released from non-fat tissue. Interleukin-6 (IL-6) is a multifunctional cytokine secreted by a number of
107 tissues including skeletal muscle. IL-6 deficient mice develop obesity late in life but also, many of the
108 beneficial effects of brown fat are not present if the brown adipose tissue is missing the *IL-6* gene.
109 Interestingly, when the calcium release channel of the sarcoplasmic reticulum (RYR1), a protein
110 implicated in non-shivering thermogenesis of skeletal muscle, is activated, the myotubes secrete IL-6
111 [22]. In addition to local effects, IL-6 can also bind to a circulating, soluble form of the IL-6 receptor
112 (IL-6R) and activate cells that do not express the membrane form of the receptor. The soluble form of
113 IL-6R has been reported to be correlated with EE and both IL-6R and IL-6 are reported to increase with
114 exercise [23] but any effect of the IL-6 pathway on food intake is not clear. Studies have identified
115 fibroblast growth factor 21 (FGF21) as a hormone involved in energy homeostasis, which increases in
116 response to fasting, low protein diets, and intense exercise, and stimulates appetite. As noted above,
117 thyroid hormone is known to act through independent pathways to increase both EE and appetite
118 and, is therefore, also a potential candidate to explain any EE-energy intake link.

119 More traditional anorexigenic and orexigenic hormones may also be important if the creation

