172 1. To investigate whether increases in 24-h EE by cold exposure lead to increased *ad libitum* food
173 intake, as measured using a vending machine paradigm.

174 2. To determine whether the effects of increased EE due to cool temperature exposure on
175 energy intake are only concomitant with the increase in EE or persist until the following day.
176 This will be explored by repeating the cool temperature exposure intervention twice: i) once
177 inside the whole-room calorimeter with an *ad libitum* diet; and, ii) once inside the whole-room
178 calorimeter during a fixed diet, followed by one day of *ad libitum* food intake on the vending
179 machines.

180 **Secondary Aims**

181 1. To determine whether 36 hrs of fasting will result in a change in energy intake on the following
182 day, and to determine whether the decrease in 24-h EE during fasting will correlate with
183 amount of food consumed the following day.

184 2. To determine if cold exposure will alter the 24-h respiratory quotient (RQ, an approximation
185 for the ratio of carbohydrate-to-fat oxidation rates), and test whether the induced RQ changes
186 independently contribute to the altered energy intake.

187 3. To determine if the 24-h EE responses to cool temperature exposure correlate with core body
188 temperature or changes in peripheral skin temperatures, and to determine if these changes
189 are related to body adiposity or associated with food intake.

190 4. To assess if behavioral testing addressing dietary restraint, stress related eating behaviors, and
191 executive function or the responses to visual analogue scales assessing hunger modify any
192 observed EE to energy intake association.

193 5. To assess whether the above behavioral testing as measured by previously validated

194 questionnaires and tasks are associated with measured food intake or hormone

195 concentrations.

196 6. To assess if concentrations of appetitive or exercise-induced hormones will correlate with the

197 observed changes in EE and energy intake.

198 7. To determine if any observed association between EE and energy intake predicts future weight

199 change at 6 months and 1 year.

200 **HYPOTHESES**

201 **Primary Hypotheses**

202 1. An increase in 24-h EE, as induced by 24 hours of exposure to 19°C, will be associated with an

203 increase in *ad libitum* food intake, which will exceed the increase in 24-h EE, on the day of the

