204 intervention and the effect will persist for at least 24 hours.

205 2. The effect of increasing EE by cool temperature exposure on *ad libitum* food intake will be

206 evident both on the day of the intervention and the following day.

207 **Secondary Hypotheses**

208 1. Thirty-six hours of fasting will induce compensatory overeating when the subject is re-

209 introduced to food, and the decrease in 24-h EE during fasting will positively predict the

210 degree of energy consumption.

211 2. The creation of an energy deficit will lead to a decrease in RQ, but the observed changes in

212 energy intake due to changes in EE will be independent of any change in RQ.

213 3. Subjects with less body adiposity will have a greater increase in 24-h EE with cool temperature

214 exposure and a greater decrease in distal skin temperatures while more obese subjects will

215 have a smaller increase in 24-h EE with cool temperature exposure and a greater decrease in

216 proximal skin temperatures indicating greater reliance on insulating mechanisms rather than
217 adaptive thermogenesis.

218 4. Measures of executive function and results of questionnaires related to eating behaviors will
219 be associated with the amount of *ad libitum* caloric intake, but the effects of EE will be
220 independent of these relationships.

221 5. Induced increases in EE will be associated with changes in hormone concentrations, including
222 cold-induced increases in adiponectin, insulin, free T4, TSH, FGF21, glucagon, ghrelin, urinary
223 free cortisol, urinary catecholamines and decreases in leptin, GLP-1, PP and PYY, and at least
224 some of these changes will be associated with the change in food intake.

225 6. The amount of energy intake increase after an increase in EE or the ratio of Δ energy
226 intake/ Δ EE will be directly associated with weight change at 6 months and 1 year.

227 **STUDY DESIGN AND METHODS**

228 **Study Design**

229 This is a inpatient natural history, observational cohort study of healthy human research
230 volunteers with research interventions designed to understand the relationship between the
231 physiologic sensing of EE and food intake behavior. This is primarily a cross-sectional study but with a
232 longitudinal component to assess the association of baseline measurements with future weight
233 change.

234 **Subjects**

235 Sixty-eight healthy participants of all body sizes representing both genders, without evidence

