517 During the approximately 23.25-h stay in the respiratory chamber, the subjects will complete a
518 Visual Analogue Scale (VAS) for measurement of appetite sensations, mood and body temperature
519 including hunger, anticipated food consumption, and desire to eat something fatty, salty, or sweet
520 [59, 60]. Subjects will complete this VAS at 3 time points: 1) prior to entering the chamber; 2) at
521 approximately 6:30 pm, prior to their evening snack; and, 3) immediately upon exiting the chamber.

522 We will use the CorTemp™ core body temperature monitoring system to assess body
523 temperature during this eucaloric feeding chamber. The system uses an ingestible, wireless sensor to
524 transmit a signal to a data recorder worn on the hip. The data recorder will be worn by volunteers for
525 the duration of the EE assessment to provide a continuous measurement of body temperature
526 change.

527 We will also ask the subjects to wear iButtons® to measure their skin temperature [61].
528 iButtons® are digital thermometers with a built-in real-time clock measuring 1.7 cm in circumference
529 and 0.6 cm in depth. They record more than 2000 consecutive temperature measurements to a 0.5°C
530 resolution which can then be downloaded to a computer. iButtons® are intended for monitoring of
531 the body temperature of humans and have been used in other studies to monitor peripheral skin

532 temperature [61, 62]. Because they are lightweight, they can be attached to the skin simply with tape.
533 Four iButtons will be used to measure distal skin temperature: two iButtons will be placed on the
534 wrist of both arms, and two iButtons will be placed at the ankles of both legs. Five iButtons will be
535 also used to measure proximal skin temperature: one cm below the navel (1°), near the left
536 paravertebral on the upper back (2°), two iButtons on the left and right supraclavicular fossa (3° and
537 4°), and one iButton near the right paravertebral at the lower back (5°).

538 **Day 7:** Upon exiting the respiratory chamber, the subjects will complete the VAS. Fasting blood will
539 then be collected for measurement of insulin, glucagon, leptin, adiponectin, ghrelin, IGF-1, active GLP-
540 1, PP, PYY, IL-6, free T3, free T4, TSH, FGF21, beta-hydroxybutyrate, lactate, pyruvate, to assess for
541 stability after a day of energy balance spent inside the metabolic chamber.

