567 provided during the vending machine assessment on the floor. Snacks, drinks, condiments and food
568 items will be stocked in a refrigerator within the respiratory chamber. A small microwave oven will be
569 available inside the chamber, just as in the vending room, for preparation of hot food items. The
570 participant will be asked to keep a record of the timing of all food consumption, and to place all waste
571 and leftover food in the air lock for weighing by the metabolic kitchen. Total energy intake will be
572 calculated as for day 7. A 24-h urine collection will again be done for nitrogen, cortisol and
573 catecholamines. Subjects will complete the VAS at 3 time points during the approximately 23.25 hours
574 inside the calorimeter. The results of this assessment will provide a measure of *ad libitum* food intake
575 inside the confined environment of the metabolic chamber at 24°C. This assessment will be used as

576 the baseline comparator for the energy intake assessment at 19°C when subjects will again be
577 confined within the metabolic chamber.

578 **Days 11, 12 and and 13:** After exiting the chamber, there will be a washout phase for any residual
579 effects of the excess food consumption expected to occur with *ad libitum* food intake to wane.
580 Subjects will be fed a weight maintaining diet.

581 ***Intervention Phase***

582 Procedures and interventions described on days 14-15 and 18 will be conducted in random order.
583 **Day 14:** Subjects will again spend approximately 23.25 hrs inside the respiratory chamber as above,
584 but this time the temperature will be set at 19°C. Prior to entering the respiratory chamber, fasting
585 blood will be collected for measurement of plasma glucose and insulin. The energy intake provided
586 during this chamber will equal the EE expended during the chamber assessment done on Day 6.

587 Standardized clothing, including shorts, a t-shirt and flip-flops will be provided for this 24-h EE
588 assessment. For sleep (from approximately 11 pm to 6 am), 3 blankets will be provided so that
589 volunteers can create their own microenvironment to achieve a level of comfort conducive to sleep. If
590 the subjects begin to shiver, they will be instructed to notify the nurse at the nurse's station and to
591 use the provided blankets until the shivering ceases.

592 The cold-induced thermogenesis (CIT, kcal/day) will be calculated as the difference between

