593 the 24-h EE at 19°C and 24-h EE at 24°C measured on Day 6. The CorTemp™ core body temperature
594 monitoring system will be used to assess changes in body temperature during this 24-h period.
595 Subjects will again be asked to wear 9 iButtons® to measure skin temperature changes during cool
596 temperature exposure. A 24-h urine collection will again be done for nitrogen, cortisol and
597 catecholamines. Subjects will complete the VAS at 3 time points during the approximately 23.25 hours
598 inside the calorimeter.

599 **Day 15:** Upon exiting the chamber, the subjects will complete the VAS. Fasting blood will be then
600 collected for measurement of insulin, glucagon, leptin, adiponectin, ghrelin, IGF-1, active GLP-1, PP,
601 PYY, IL-6, free T3, free T4, TSH, FGF21, estradiol and progesterone, beta-hydroxybutyrate, lactate,
602 pyruvate. Subjects will again spend 24 hrs using the vending machine paradigm, as above, for the
603 assessment of *ad libitum* food intake following the increased EE resulting from the cold-induced
604 thermogenesis during Day 14.

605 **Day 16 and 17:** This will be a wash-out period for any residual effects of the overeating expected to
606 occur during *ad libitum* food intake to wane [10]. Subjects will be fed a weight maintaining diet.

607 **Day 18:** Subjects will again reside for approximately 23.25 hrs in the respiratory chamber in a cool
608 environment (19°C), this time with access to food choices similar to those provided during the
609 assessment on Day 10. A 24-h urine collection will again be done for nitrogen, cortisol and
610 catecholamines. Subjects will complete the VAS at 3 time points during the approximately 23.25 hours
611 inside the calorimeter.

612 The amount of food intake on Day 18, as well as on Day 15, will help to determine the length
613 of time in which the cold-induced increase in EE might affect food intake, i.e. whether any EE-effect
614 on energy intake only occurs during cooler temperature exposure or whether the effect persists until
615 the following day. The amount of food intake consumed inside the metabolic chamber on Day 18 at
616 19° C will be compared to that obtained on Day 10 at 24°C in the same setting to evaluate the
617 difference in energy intake during the cool temperature exposure.

618 **Days 19 and 20:** This will be a washout period for any residual effects of the overeating expected to

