619 occur with *ad libitum* food consumption to wane. Subjects will be fed a weight maintaining diet.

620 **Day 21:** Subjects will spend approximately 23.25 hrs inside the respiratory chamber at 24°C but with
621 no food intake, for assessment of 24-h EE while fasting. Water will be provided and volunteers will be
622 encouraged to stay well-hydrated. Prior to entering the respiratory chamber, fasting blood will be
623 collected for measurement of plasma glucose and insulin. A 24-h urine collection will again be done
624 for nitrogen, cortisol and catecholamines. The CorTemp™ core body temperature monitoring system
625 will be used to assess changes in body temperature during fasting. Subjects will again be asked to
626 wear 9 iButtons® to measure skin temperature changes during fasting. Subjects will complete the
627 VAS at 3 time points during the 24 hours inside the calorimeter.

628 **Day 22:** Upon exiting the chamber, the subjects will complete the VAS. Fasting blood will be then
629 collected for measurement of insulin, glucagon, leptin, adiponectin, ghrelin, IGF-1, active GLP-1, PP,
630 PYY, IL-6, free T3, free T4, TSH, FGF21, estradiol and progesterone, beta-hydroxybutyrate, lactate,
631 pyruvate. Subjects will spend 24-h using the vending machine paradigm on the floor, as above. The
632 results of this vending machine assessment will be used to ascertain the amount of intake following a
633 maximal energy deficit, as a baseline comparison.

634 **Day 23:** Participants will complete the vending machine exit questionnaire, an 11-item questionnaire
635 designed by our staff to assess motivation to eat while using the vending machines. This *ad hoc*
636 questionnaire includes items related to mood, liking of food, and timing of meals. Subjects will then
637 be discharged home.

638 **Outpatient Visits**

639 Volunteers will be invited to return after 6 months and 1 year from the date of discharge. On
640 these visits, vital signs and weight data will be obtained. Volunteers will also have an assessment of
641 body composition by DXA and will be administered the IPAQ and FFQ questionnaires to have
642 measures of physical activity and dietary intake, respectively, during the follow-up period. Fasting

643 blood collection will be done for measurement of complete blood cell count, platelet count, glucose,
644 electrolytes, plasma urea nitrogen, creatinine, liver function tests, thyroid profile as well as plasma

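### Day 15 intake cannot separate compensation for a cold-induced deficit from a lasting EE signal, and the persistence of a free-eating rise (Hypothesis 1) is never observed

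*Combined protocol and SAP*

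**What the plan says.** All references are to the combined protocol and SAP.

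- **Primary Aims, Aim 2** asks whether the effects of raised EE on "energy intake are only concomitant with the increase in EE or persist until the following day". The next-day arm is openly specified as a cold session in the "calorimeter during a fixed diet, followed by one day of *ad libitum* food intake on the vending" machines.
- **Primary Hypotheses, Hypothesis 1** predicts that free intake on the cold day will rise by more than EE does. It ends: "intervention and the effect will persist for at least 24 hours". Hypothesis 2 expects the effect of raised EE on both the cold day and the next day.
- **Intervention Phase, Day 14 (19°C)**: the energy provided "during this chamber will equal the EE expended during the chamber assessment done on Day 6". CIT is defined as 24-h EE at 19°C minus Day 6 EE.
- **Intervention Phase, Day 18 (19°C, free eating)**: intake on this day and on Day 15 is to help establish the length "of time in which the cold-induced increase in EE might affect food intake, i.e. whether any EE-effect" occurs only in the cold or lasts to the next day.
- **Intervention Phase, Days 19 and 20**, after Day 18: "Subjects will be fed a weight maintaining diet".
- **Table 4** lists ad libitum intake on Days 7-10, 15, 18 and 22 only.

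**The concern.** Hypothesis 1 describes one effect followed over time: people eat more while cold, and go on eating more the next day. Testing it needs free intake on the day after a free-eating cold day, and no such day is measured. The two cold sessions are run in random order, but that only swaps them. It does not add a free-eating day after the ad libitum session.

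Day 15 follows a different kind of cold day, one on which participants could not eat in response to the cold. Days 18 and 15 therefore differ in prior energy balance as well as in timing. The Introduction treats this distinction as open. It names a deficit-driven hunger signal ("energy intake would persist. For example, the energy deficit created by the cold-induced" thermogenesis) and, separately, a direct EE effect that might or might not outlast the cold.

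If intake rises on both days, the natural report is that the effect occurs in the cold and then persists. The same data would arise if people replace the deficit as soon as they are allowed to, with nothing carried over after a cold day of free eating.

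**Working it through.** The plan gives no figure for this point, so the check is mainly structural. The sample size used in step 3 does reproduce: the Fisher z formula for r = 0.40, two-sided alpha 0.01 and power 0.80 gives n = 68.07, against the stated 68. This point does not affect it.

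**1. Energy balance on Day 14, if all food is eaten.**
- Intake on Day 14 = EE on Day 6 (Day 14 text).
- CIT = EE on Day 14 − EE on Day 6 (Day 14 text).
- Balance on Day 14 = intake − EE = EE on Day 6 − EE on Day 14 = −CIT.

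The change in EE and the absolute Day 14 deficit are the same number for each person.

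**2. Size of the deficit.** The inputs are the Day 1 equations for weight-maintaining needs, the 80% chamber diet (Day 6) and the 5-15% EE rise (Introduction). Taking Day 6 EE as 80% of weight-maintaining needs is an assumption.

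| Participant | Needs (kcal) | × 0.80 | 5% | 15% |
|---|---|---|---|---|
| Woman, 60 kg | 9.5 × 60 + 1745 = 2315 | 1852 | 93 | 278 |
| Man, 80 kg | 9.5 × 80 + 1973 = 2733 | 2186 | 109 | 328 |
| Man, 120 kg | 9.5 × 120 + 1973 = 3113 | 2490 | 125 | 374 |

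Full repayment (a second assumption) predicts a Day 15 rise of these sizes with no lasting EE signal.

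**3. Can Day 15 tell the two routes apart?** This was simulated with n = 68 and 4,000 runs. Assumed values were CIT with mean 210 and SD 100 kcal, and intake noise with SD 229 kcal. The last column is a hypothetical free-eating day after Day 18. It assumes that cold-day intake rose by 1.1 × CIT, in line with Hypothesis 1.

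| True mechanism | Day 15: r with CIT | Day 15: mean change | Day after Day 18 (not measured) |
|---|---|---|---|
| Pure deficit repayment | 0.396 | +210 kcal | −21 kcal |
| Pure lasting EE signal | 0.398 | +210 kcal | +210 kcal |

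The last column follows by hand: 210 − 1.1 × 210 = −21 under repayment, and 210 under a lasting signal. The mechanisms agree on the day that is measured and part on the day that is not.

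**The case against.** The strongest reply is that Aim 2 concerns the effects of raised EE on intake and names the fixed-diet sequence as its own test. The Introduction counts deficit-driven hunger as one way an effect could outlast the cold, and Hypothesis 2 can be read in the same broad sense. A deficit-mediated rise on Day 15 would then be a valid positive answer. This stands. A reader might infer that Aim 2 would be answered wrongly, or that Day 15 measures repayment rather than persistence. The documents support neither, because a lasting direct signal would also appear on Day 15.

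A reader might also infer that no analysis could ever separate the routes. That goes too far, for two reasons.
- The identity in step 1 concerns the absolute Day 14 deficit. If Day 15 is compared with Day 7, the change in prior-day balance is −CIT minus the Day 6 balance, and on an 80% diet the Day 6 balance need not be zero. The Introduction describes balance within 20% in an earlier study. If that applied here (an assumption), 20% of 2186 is ±437 kcal, wider than the CIT range for the same man.
- The fasting sequence (Days 21-22) imposes a large deficit while EE is expected to fall, so it offers a reference for deficit-driven eating.

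Neither route is planned, however. Data Analysis lists no adjustment for energy balance and no use of the fasting result to interpret Day 15. The planned hormone, RQ and appetite mediation models may inform mechanism, but they do not supply the missing intake day.

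Finally, fixing Day 14 intake is a defensible trade-off. The protocol expects overeating on free-eating days, and a free-eating day after Day 18 would carry that surplus. The Day 18 text also says only that the two intakes will help to determine duration; it sets no formal rule. These points limit the criticism to the inference drawn. They do not make Hypothesis 1's persistence claim testable.

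**Conclusion.** The point holds as confounding and a limit on inference. Day 15 mixes compensation for an unmet cold-induced deficit with a direct EE signal that outlasts the cold. The design cannot test Hypothesis 1's claim that a freely expressed intake rise lasts at least 24 hours, and Days 18 and 15 together do not trace one effect over time. A Day 15 rise remains a legitimate answer to Aim 2 as a next-day response to raised EE.

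The deficit identity assumes that all Day 14 food is eaten. The 109-328 kcal figure is illustrative: it assumes an 80 kg man, Day 6 EE at 80% of weight-maintaining needs, and full repayment. Across 60-120 kg the range is 93-374 kcal. The simulation's CIT and noise values are also assumptions, but the Day 15 equivalence follows from the identity and not from those values.

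**What to change.** Change the wording in four places: Primary Aim 2, Hypotheses 1 and 2, and the Day 18 text.

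- Describe the Day 15 result as *the next-day intake response after a cold day with fixed intake, that is, after an uncompensated cold-induced deficit*.
- In Hypothesis 1, limit the prediction for the free-eating rise to the cold day itself, and state the next-day prediction separately in the terms above.
- In the Day 18 text, remove the inference that Days 18 and 15 together show how long a freely expressed intake effect, or a direct EE signal, lasts.

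The cost is a narrower claim on a primary aim. No new visit, sample or participant is needed.

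Hunger ratings on chamber exit should not be made a decision rule for persistence. The Day 6 text places the last rating "approximately 6:30 pm, prior to their evening snack; and, 3) immediately upon exiting the chamber", so contrasts of Day 18 with Day 10 and of Day 14 with Day 6 look available if that timing applies throughout. But overeating on Day 18 could suppress exit hunger despite a true EE signal. Day 10 also follows three free-eating days, whereas the Day 18 session follows weight-maintaining days, and Table 4 classes these ratings as descriptive or a possible mediator. They can be reported as supportive only.
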